### **2.1 Primary Objectives**

To determine the safe reduction of the number of fractions (10, 8, or 5), that may be delivered safely in resected HNSCC patients with intermediate pathologic risk features.

### **2.2 Secondary Objectives**

1. To evaluate the efficacy of the HART-HN regimen at the minimum number of safe fractions at 1-year as measured by locoregional control and overall survival
2. To assess patient quality of life during and after the HART-HN regimen at the minimum number of safe fractions as measured by a battery of patient quality of life and functional metrics.

### **2.3 Primary Endpoint**

The primary endpoint of the study is to find the maximum tolerated dose density for radiation regimens with a BED3 = 100 Gy, that may be safely delivered for the HART-HN regimen in patients with resected HNSCC with intermediate pathologic risk features.

### **2.4 Secondary Endpoint(s)**

1. 1-year locoregional control of patients receiving HART-HN (efficacy objective)
2. 1-year overall survival of patients receiving HART-HN (efficacy objective)
3. Temporal changes in the CTCAE version 5.0 scores (quality of life objective)
4. Temporal changes in composite FACT-HN scores, composite MDADI scores, opioid use, EAT-10 questionnaire scores, Functional Oral Intake (FOIS) scores and Dynamic Imaging Grade of Swallowing Toxicity (DIGEST) grading (quality of life objective)

## 3 STUDY DESIGN

### 3.1 General Description

We propose a pilot Phase I study using a Time-to-Event Continuous Reassessment Methodology (TITE-CRM) design to estimate the minimum number of safe fractions. Patients with resected head and neck squamous cell carcinomas and no evidence of measurable disease with indications for adjuvant radiation alone and a life expectancy of at least 12 months will be enrolled. Patients with extracapsular extension and/or positive margins will be excluded due to data from multiple randomized trials suggesting a benefit for concurrent chemotherapy in this population. Baseline symptom evaluation will be obtained using validated surveys of head and neck cancer patients: the Functional Assessment of Cancer Therapy for the Head and Neck (FACT-HN) and the MD Anderson Dysphagia Inventory for Head and Neck (MDADI-HN). Patients will then undergo treatment using HART-HN and will subsequently be followed for up to 1 year.

Adjuvant radiation is the experimental therapy in this study, which will be the subject of fraction reduction while maintaining a BED3 of approximately 100 Gy. The minimum number of safe fractions will be determined as the radiation dose fractionation scheme with the least number of fractions at which there is no more than a 33% rate of dose-limiting toxicity (DLT) up to one year after treatment (to allow for the development of late toxicities from radiation).

All patients will receive a course of radiation therapy to the operative bed and regional elective using image-guided intensity modulated radiation therapy as detailed in section 5.1.

Patients will undergo standard consultation to receive adjuvant head and neck radiotherapy for HNSCC and will be determined to be eligible for the clinical trial. If eligible, patients will receive informed consent about the risks and benefits of the trial and if they accept, will sign confirming their enrollment. Patients will then undergo standard radiotherapy simulation including CT simulation with and without IV contrast and/or MRI simulation with and without Gadolinium contrast. Patients will complete baseline FACT-HN and MDADI surveys. Patients will also be followed with a speech and language pathologist (SLP) and undergo videofluoroscopic swallow studies (VFSS) prior to treatment, 3 months after treatment and 6 months after treatment, as is standard of care in the treatment of HNSCCs and will be graded by the Dynamic Imaging Grade of Swallowing Toxicity (DIGEST) scale.

A radiation treatment plan will be developed as per the details in Section 5.1 with two target volumes: the PTV\_High (defined as the operative bed plus a 3 mm margin) will receive the experimental dose over the experimental number of fractions (BED3 of ~100, the BED3 of 60 Gy in 30 fractions) and the PTV\_Low (elective lymph node regions plus 3 mm setup margin) will receive a subclinical dose over the experimental number of fractions (BED3 of ~86.4, the BED3 of 54 Gy in 30 fractions).

Patients will then undergo daily image-guided radiotherapy on a Monday-Friday basis for the total number of experimental fractions. During treatment, all patients will be evaluated for acute toxicities at least once every five fractions with a physician visit. Additionally, patients will complete repeat FACT-HN and MDADI surveys on the day of treatment review.

After completion of the HART-HN, patients will be seen in follow-up at the following time points after completion of radiotherapy: bi-weekly for the first 6 weeks, at 3 months, 6 months, 9 months and 12 months. Patients will complete repeat FACT-HN and MDADI surveys to assess for quality of life outcomes at each follow-up. Repeat imaging including a PET/CT or Chest CT (with or without contrast) and a diagnostic CT (with or without contrast) or MRI of the neck will be ordered at the 3-month (+/- 2 weeks) follow-up timepoint. A head and neck CT or MRI may be ordered at any time, if clinically indicated.

To assess efficacy of the HART-HN regimen assessment of locoregional control and overall survival will be made by the treating radiation oncologist or surgeon at each follow-up, by clinical examination of the head and neck as per the standard of care. Standard post-treatment imaging including a neck CT (with or without contrast) or MRI and a chest CT (with or without contrast) or PET/CT (with or without contrast) will be obtained at 3 months post-treatment (+/- 2 weeks), as per standard of care. Additional surveillance imaging in the follow-up setting has not shown any benefit in 3-year disease-free survival as compared to ongoing clinical surveillance. Therefore, patients will be clinically followed for disease control until locoregional progression, completion of the 12-month follow-up period, patient refusal, or death.

In order to understand the acute and long-term toxicities of the HART-HN regimen patients will be followed clinically by the treating radiation oncologist, undergo routine FACT-HN and MDADI surveys, and undergo scheduled SLP visits including VFSS and DIGEST grading as detailed in the prior section. For the purposes of this study, acute toxicity will be deemed any toxicity that occurs within 90 days of completion of radiation therapy, and late toxicity will be deemed any toxicity that occurs more than 90 days after completion of radiation therapy. During each weekly treatment review and each post-treatment follow-up, the treating physician will record a pain score (scale 1-10) and use the Common Terminology Criteria for Adverse Events Version 5.0 (CTCAE) to record toxicity scores for dysphagia, oral mucositis, dehydration and weight loss. The treating physician will also record tracheostomy tube dependence and feeding tube dependence at each visit.

### 3.2 Study Completion

The study will reach study completion approximately 24 months from the time the study opens to accrual.

## 4 SUBJECT PARTICIPATION, DISCONTINUATION, AND WITHDRAWAL

MCW must follow all MCW IRB requirements and policies regarding subject participation, found here: <https://www.mcw.edu/HRPP/Policies-Procedures.htm>

This study protocol will be available at the Clement J. Zablocki Veterans Affairs Medical Center (CJZVAMC) where local VA IRB requirements and policies will also be followed: [https://www.research.va.gov/resources/policies/human\\_research.cfm](https://www.research.va.gov/resources/policies/human_research.cfm)

### 4.1 Subject Status

Subject statuses throughout the trial are defined as follows:

- Prescreening: preconsent (subject considering trial or study staff considering patient for the trial per institutional recruitment methods).
- Screening: period after consent, but prior to eligibility confirmation.
- Consented: consented, prior to eligibility confirmation.
- Eligible: the local investigator confirms all eligibly criteria apply.
- On study/enrolled: date eligibility is confirmed.
- On arm: date of enrollment.
- On treatment: first day treatment was given to the last day treatment was given.
- Off treatment: the last day treatment was given.
- On follow-up: from last day of treatment to the end of follow-up period.
- Off study: follow-up period completed, with no additional data gathered.
- Withdrawn: subject fully withdraws consent (i.e., refuses ALL follow-up, even survival) or is taken off study by the local principal investigator.

## **4.2 Prescreening and Screening Log**

The MCW study principal investigator regularly reviews screen failure reasons to understand barriers to accrual and consider amending eligibility criteria. Screen failures are defined as participants who were considered for the trial to participate in the clinical trial with or without consent, but are not subsequently assigned to the study intervention or enrolled in the study. This study will follow our departmental and institutional SOPs regarding prescreening and screening tracking.

## **4.3 Consent**

Investigators or their appropriate designees will identify potentially eligible subjects from their clinics, subject self-referrals, referrals from other clinicians, and/or other IRB-approved recruitment methods. No study conduct, including subject prescreening, can occur until after IRB approval.

A written, signed informed consent form (ICF) and a Health Insurance Portability and Accountability Act (HIPAA) authorization must be obtained before any study-specific assessments are initiated. A signed ICF copy will be given to the subject and a copy will be filed in the medical record (per local IRB policies and SOPs). The original will be kept on file with the study records.

## **4.4 Screening Procedures**

Refer to study calendar of events.

Visit procedures that were performed as standard of care prior to consent (without the specific intent to make the subject eligible for the trial), may count toward screening tests and eligibility if they are within the screening window.

## **4.5 Registration Procedures**

Study staff must adhere to MCWCC CTO SOPs regarding eligibility review/confirmation.

No waivers of protocol eligibility will be granted. When clinical factors relating to an eligibility item are unclear or questionable, the MCW PI can only provide guidance or clarification on eligibility. Any eligibility questions should be directed to [name] ([[contact]](mailto:[contact])) or [name] ([[contact]](mailto:[contact])).

## 4.6 Eligibility Confirmation

Subject Initials: \_\_\_\_\_ Subject Study ID: \_\_\_\_\_

### Inclusion Criteria

1. Patients 18 years or older with gross totally resected (R0 resection) HPV-negative squamous cell carcinoma of the head and neck (squamous cell carcinoma of the larynx, hypopharynx, oropharynx, oral cavity, nasal cavity, paranasal sinuses or carcinoma of unknown head/neck primary) who have at least 1 of the following intermediate risk factors for adjuvant radiation:
  - a) **Pathologic Node Positive Disease**
  - b) **Perineural Invasion**
  - c) **Oral cavity cancer with depth of invasion of at least 5 mm**
  - d) **Lymphovascular Space Invasion**
  - e) **Pathologic T3 or T4 disease**
2. Zubrod performance status 0-2.
3. Patients must have the psychological ability and general health that permits completion of the study requirements and required follow up.
4. Inclusion of Covid-19 positive patients will be based on standard institutional protocol.
5. Female patients must meet one of the following:
  - Postmenopausal for at least one year before the screening visit, or
  - Surgically sterile (i.e. undergone a hysterectomy or bilateral oophorectomy), or
  - If subject is of childbearing potential (defined as not satisfying either of the above two criteria), agree to practice two acceptable methods of contraception (combination methods requires use of two of the following: diaphragm with spermicide, cervical cap with spermicide, contraceptive sponge, male or female condom, hormonal contraceptive) from the time of signing of the informed consent form through 90 days after the last dose of study agent, AND
    - Agree to practice true abstinence when this is in line with the preferred and usual lifestyle of the subject. (Periodic abstinence [e.g., calendar, ovulation, symptom-thermal, post ovulation methods] and withdrawal are not acceptable contraception methods).
6. Male patients, even if surgically sterilized (i.e., status post vasectomy), must agree to one of the following:
  - Practice effective barrier contraception during the entire study period and through 60 calendar days after the last dose of study agent, OR
  - Must also adhere to the guidelines of any study-specific pregnancy prevention program, if applicable, OR
    - Agree to practice true abstinence when this is in line with the preferred and usual lifestyle of the subject. (Periodic abstinence [e.g., calendar, ovulation, symptom-thermal, post ovulation methods] and withdrawal are not acceptable methods of contraception.)
7. Ability to understand a written informed consent document, and the willingness to sign it.

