### Exclusion Criteria

A potential subject who meets any of the following exclusion criteria is ineligible to participate in the study.

1. Pathologic evidence of extranodal extension.
2. Pathologic evidence of a final positive margin (R1 resection) or gross residual disease (R2 resection).
3. HPV-positive squamous cell carcinoma.
4. Prior invasive malignancy within the past 3 years (except for non-melanomatous skin cancer, and early stage treated prostate cancer).
5. Life expectancy less than 12 months.

6. Performance status Zubrod  $\geq 3$ .
7. Patients with prior radiation therapy to the head and neck. Note: Prior external beam radiotherapy is excluded, but Iodine 131 is allowed.
8. Prior systemic therapy, including cytotoxic chemotherapy, biologic/targeted therapy, or immune therapy for the study cancer.
9. Body weight  $\leq 30$  kg.
10. Any of the following severe laboratory abnormalities within 14 days of registration, unless corrected prior to it: Sodium  $< 130$  mmol/L or  $> 155$  mmol/L; Potassium  $< 3.5$  mmol/L or  $> 6$  mmol/L; Fasting glucose  $< 40$  mg/dl or  $> 400$  mg/dl; Serum calcium (ionized or adjusted for albumin)  $< 7$  mg/dl or  $> 12.5$  mg/dl; Magnesium  $< 0.9$  mg/dl or  $> 3$  mg/dl.
11. Unstable angina and/or congestive heart failure requiring hospitalization within 3 months prior to Step 1 registration.
12. Transmural myocardial infarction within 3 months prior to Step 1 registration.
13. Medical or psychiatric illness which would compromise the patient's ability to tolerate treatment or limit compliance with study requirements.
14. Pregnancy or women of childbearing potential and men who are sexually active and not willing/able to use medically acceptable forms of contraception during treatment and for 6 months after radiation, this exclusion is necessary because the treatment involved in this study may be significantly teratogenic. Women who are breastfeeding are also excluded.

*"I have reviewed all inclusion and exclusion criteria and confirm the subject is eligible."*

---

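### The eligibility form gives women two contraception end dates, 90 days and 6 months after treatment, and joins inclusion item 5's abstinence clause with AND where OR appears to be meant

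*Combined protocol and SAP*

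**What the plan says.** Section 4.6, Inclusion Criteria, item 5 accepts a woman who is postmenopausal, surgically sterile, or of childbearing potential and willing to use two methods from a named list. The agreement runs "from the time of signing of the informed consent form through 90 days after the last dose of study agent, AND". The clause that follows reads "Agree to practice true abstinence when this is in line with the preferred and usual lifestyle of the subject". A parenthesis then rejects periodic abstinence and withdrawal as methods.

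Item 6 offers men alternatives. The first is "Practice effective barrier contraception during the entire study period and through 60 calendar days after the last dose of study agent, OR". The second, "Must also adhere to the guidelines of any study-specific pregnancy prevention program, if applicable, OR", leads into the same abstinence clause.

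Exclusion item 14 covers pregnancy and "women of childbearing potential and men who are sexually active and not willing/able to use medically acceptable forms of contraception". Its period is "during treatment and for 6 months after radiation, this exclusion is necessary because the treatment involved in this study may be significantly teratogenic". The Exclusion Criteria open with "A potential subject who meets any of the following exclusion criteria is ineligible to participate in the study", and the form closes with one attestation covering both lists. Section 4.5 adds "No waivers of protocol eligibility will be granted", though the principal investigator may give guidance where clinical factors behind an item are unclear.

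**The concern.** Item 5 and exclusion item 14 both set how long a woman should avoid pregnancy after this treatment, and they give different answers. Nothing in the protocol reconciles them. Item 5 is the more operational text: it names the methods, the start and the end, and records what the woman agrees to. Someone counselling from item 5 alone would give about half the period that exclusion item 14 ties to teratogenic risk. The study calendar schedules a pregnancy test at screening only, so no planned on-study test would pick up a patient who stopped early.

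The connector is a separate matter. With AND, the abstinence clause adds to the two-method agreement instead of replacing it. A woman whose usual lifestyle is abstinence, and who sees no reason to agree to two methods, fails item 5 as written, and no waiver is available.

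**Working it through.** The plan states no figure on this point that could be reproduced. The check is a comparison of the two criteria, followed by calendar arithmetic.

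**Step 1. The two criteria side by side.**

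| | Inclusion item 5 | Exclusion item 14 (women) |
|---|---|---|
| What is asked | Two methods from a named list | Medically acceptable contraception; no number or list |
| Start | Signing of consent | Treatment |
| End | 90 days after the last dose | 6 months after radiation |
| Reason given | None | Possible teratogenicity |

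The end dates have in effect the same anchor. Section 3.1 names adjuvant radiation as the experimental therapy and no study drug is given, so the last dose in item 5 can only be the last fraction.

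**Step 2. Size of the gap.** Gap = days in 6 calendar months − 90.

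- Shortest case, for example 1 September to 1 March in a non-leap year: 30 + 31 + 30 + 31 + 31 + 28 = 181 days; 181 − 90 = 91.
- Longest case, for example 1 March to 1 September: 31 + 30 + 31 + 30 + 31 + 31 = 184 days; 184 − 90 = 94.
- Every start date from 2021 through 2028 gives 181, 182, 183 or 184 days, so the gap is always 91 to 94 days.
- Share of the 6 months covered by 90 days: 90/184 = 48.9% to 90/181 = 49.7%.
- If a month is counted as 30 days, the gap is 180 − 90 = 90 days.

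**Step 3. Which period binds.** Meeting any exclusion makes a patient ineligible. A sexually active woman of childbearing potential who would accept 90 days but not 6 months satisfies item 5, meets exclusion item 14, and cannot enrol. The longer period therefore binds.

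**Step 4. The connector.** Item 5 for a woman of childbearing potential has the form: two methods AND abstinence where usual. For an abstinent woman both parts apply. Item 6 for men has the form: barrier method OR prevention programme OR abstinence where usual, so abstinence is enough. Item 5's own parenthesis turns away only periodic abstinence and withdrawal, which suggests that true abstinence was meant to be acceptable.

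**Step 5. Would correcting the connector be enough?** In exclusion item 14 the condition of being sexually active may attach to both women and men, or to men only. On the first reading an abstinent woman is outside the exclusion. On the second she is excluded if she will not use contraception, whatever item 5 says. The wording does not settle it, so item 14 needs attention too.

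**The case against.** The strongest reply is that the criteria are cumulative rather than contradictory. A woman can meet both by using two listed methods from consent to day 90 and any acceptable contraception from then to 6 months. The methods asked for and the start dates differ as well as the end dates, so a stepped scheme is possible. This stands in part: it shows that both criteria can be satisfied, and that simply replacing 90 days by 6 months in item 5 would extend the two-method demand beyond anything now required. But no text describes a stepped scheme, and a reader of item 5 would not know that contraception continues.

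The abstinence reading can also be called over-literal. The clause is conditional, the OR in item 6 shows the likely intent, and eligibility questions can be referred for guidance. That is fair as to likely practice. The guidance provision, however, speaks of unclear clinical factors, and a wrong connector is better corrected in the text.

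Four stronger inferences are tempting and are not supported:

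- *Women may stop at day 90.* They may not; exclusion item 14 still requires 6 months.
- *Item 5 is the only criterion that reaches an abstinent woman.* That depends on one of the two readings in step 5. Only the demand for two listed methods is certainly peculiar to item 5.
- *Men are short by 121 to 124 days, from 60 days against 6 months.* Item 6 counts the whole study period as well as the 60 days. Section 4.1 places a subject off study only when follow-up is complete, so a period of 12 months or more is plausible. No shortfall for men is shown.
- *Patients are told the wrong period.* That depends on the consent form, which was not among the material reviewed.

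**Conclusion.** The point holds as a low-severity inconsistency in the eligibility and fetal-safety wording. The form carries two end dates, 91 to 94 days apart, for women's contraception after the same treatment, with the 6-month rule prevailing. Item 5's AND, read literally, asks an abstinent woman for two contraceptive methods and is probably a slip.

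The conclusion assumes that the last dose of study agent means the last radiation fraction and that months are calendar months. The number of women of childbearing potential is not given; with 18 patients in all, few are likely to be affected. A pregnancy after day 90 would still be captured, because Section 6.1.2 lists pregnancy as a serious adverse event and Section 6.2.1 collects events through the 12-month follow-up. There is no effect on DLT assessment, dose assignment or the TITE-CRM analysis.

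**What to change.** - **Item 5, period.** State that contraception continues through 6 months after the last radiation fraction, to match exclusion item 14. Have the sponsor say whether two methods are required throughout, or only to day 90 with medically acceptable contraception after that. The first choice tightens entry for women who are not abstinent, so it should be made openly.
- **Item 5, connector.** Change AND to OR before the abstinence clause.
- **Exclusion item 14.** Make clear that the condition of being sexually active applies to women as well as men, so that an abstinent woman accepted under item 5 is not then excluded.
- **Consent form.** Check that it states the same period.

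Item 6 needs no change on the error shown. The cost is a short amendment to two criteria, which needs IRB approval under Section 9.5.3, and one check of the consent form. No visits, tests or patients are added.
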